Study Co-ordinator	[name] [name], MD, PhD. Mail: Division of Neurosurgery, [name] [contact] E-mail: [contact] [contact]
Sponsor	[name], R&D Manager Mail: Cambridge University Hospitals NHS Foundation Trust, [name] [contact] E-mail: [contact] [contact]
Joint-sponsor(s)/co-sponsor(s)	University of Cambridge, Cambridge, United Kingdom
Funder(s)	Swedish Society of Medicine
Key Protocol Contributors	N/A
Committees	N/A

Directed management in brain injury.

STUDY SUMMARY

Study Title	Multimodality Monitoring Directed Management of Patients Suffering from Traumatic Brain Injury
Internal ref. no. (or short title)	Directed management in brain injury
Study Design	Controlled trial without randomisation
Study Participants	Patients with traumatic brain injury and need for intracranial monitoring.
Planned Size of Sample (if applicable)	100
Follow up duration (if applicable)	6 months
Planned Study Period	5 years
Research Question/Aim(s)	
Primary aim:
 
Establish and validate a clinical protocol for microdialysis derived chemistry driven therapy in TBI and see if it improves lactate:pyruvate ratio (<25).
 
Secondary aims:
 
Determine the optimal strategies for correcting abnormalities in microdialysis derived parameters.
 
Determine the inflammatory, tissue and functional outcome for patients suffering from different defined pathological conditions

Directed management in brain injury.

FUNDING AND SUPPORT IN KIND

FUNDER(S) (Names and contact details of ALL organisations providing funding and/or support in kind for this study)	FINANCIAL AND NON FINANCIAL SUPPORT GIVEN
Swedish Society of Medicine	214.000 SEK (Swedish Krona ~ 20.000£)

Directed management in brain injury.

ROLE OF STUDY SPONSOR AND FUNDER

The study sponsor will guarantee that the study will be performed according to rules and regulations, and will assume overall responsibility for the initiation and management of the study.

The Funder will guarantee salary for [name]. The funder will have no role in study design, conduct, data analysis and interpretation, manuscript writing, and dissemination of results.

Neither sponsors nor funder will have control over the final decision regarding any of these aspects of the study.

Directed management in brain injury.

ROLES AND RESPONSIBILITIES OF STUDY MANAGEMENT COMMITTEES/GROUPS & INDIVIDUALS

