4 RESEARCH QUESTION/AIM(S)

Primary aim:

Establish and validate a clinical protocol for microdialysis derived chemistry driven therapy in TBI and see if it improves lactate:pyruvate ratio (<25).

Secondary aims:

Determine the optimal strategies for correcting abnormalities in microdialysis derived parameters.

Determine the inflammatory, tissue and functional outcome for patients suffering from different defined pathological conditions

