4.1 Objectives

1. We wish to determine which of the provided therapies that was superior to others in improving the deranged brain metabolism.
2. We also wish to determine the inter-relationships between parameters detected using the microdialysis and other monitoring techniques, such as brain oxygen saturation and perfusion pressure in the damaged brain, and how microdialysis may complement these techniques.
3. How the protocol will alter cytokine, chemokine and markers of brain damage markers (S100B) in serum and microdialysate for patients suffering from different pathological states?
4. How will the functional outcome distribution be for patients suffering from different pathological states?

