4.2 Outcome

Improvement of lactate/pyruvate ratio <25 (by different treatment strategies).

5 STUDY DESIGN and METHODS of DATA COLLECTION AND DATA ANALYSIS

Multimodality monitoring parameters that will be included:

Directed management in brain injury.

a) Standard monitoring

Intracranial pressure

Cerebral perfusion pressure (mean arterial pressure – intracranial pressure)

Brain tissue oxygen tension

Pressure reactivity index (PRx)

Therapy intensity levels

b) Microdialysis parameters

Metabolic intermediaries (lactate, pyruvate, glucose, glutamate, glycerol)

Cytokine analysis

Nitric oxide

c) CSF parameters

Cytokines and chemokines

d) Serum

Circulating cytokines, chemokines, tissue damage markers (S100B)

The monitoring data will be stored automatically. The chemokine, cytokine and tissue damage marker samples will be analysed using commercially available LUMINEX kits by members of the research team.

Standardized questionnaires to assess extended Glasgow Outcome Score (eGOS) as well and Short Form 36 (SF-36) will be used during the follow-up appointment in the outpatient clinic by members of the research team.

Data will be analysed by members of the research team using comparative statistics between patients with different pathological targets. The statistical program R will be used.

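### The study is labelled a controlled trial, but it has no comparator for the algorithm or for its individual therapies, so its effect and superiority aims cannot be answered

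*Protocol*

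**What the plan says.** The Study Summary gives the study design as "Controlled trial without randomisation". The primary aim, there and in section 4, is to "Establish and validate a clinical protocol for microdialysis derived chemistry driven therapy in TBI and see if it improves lactate:pyruvate ratio (<25"). The first secondary aim is to "Determine the optimal strategies for correcting abnormalities in microdialysis derived parameters". In section 4.1, objective 1 reads "We wish to determine which of the provided therapies that was superior to others in improving the deranged brain metabolism", and objective 3 asks "How the protocol will alter cytokine, chemokine and markers of brain damage markers (S100B") in different pathological states. Section 4.2 gives the outcome as "Improvement of lactate/pyruvate ratio <25 (by different treatment strategies").

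The body of the Protocol describes something else. Section 3 puts all patients on the same protocol and says that this minimises selection and researcher bias. Section 6 describes a single-centre prospective study of one new algorithm. The only analysis named in section 5 is "comparative statistics between patients with different pathological targets", and section 7.2.1 ties the sample size of 100 to that same comparison.

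**The concern.** A controlled trial, randomised or not, needs a group or period that shows what happens without the intervention. Sections 8 and 8.1 point to the natural contrast: the same treatments given conventionally, without the structured algorithm. Nothing in the Protocol measures it.

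Two kinds of claim are at stake. The first is whether the algorithm lowers LPR. The second is which therapy works best. Under the stated label, a reader would take a fall in LPR as an effect against a control, and a difference between therapies as evidence that one is better. The design supports neither reading.

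**Working it through.** **1. Is there a control?** The places that could define one are these:

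| Place | Content | Control for the algorithm? |
|---|---|---|
| Study Summary | Controlled, not randomised | Claimed, not described |
| Section 3 | All patients on one protocol | No |
| Section 5 | Comparison by pathological target | No, all are treated |
| Section 6 | One centre, one new algorithm | No |
| Section 7.2.1 | 100 patients, for a difference between pathological targets | No |

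The figure of 100 cannot be reproduced: no effect size, variance, power or group sizes are given. In any case it concerns pathologies, not algorithm against control.

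**2. Can therapies be compared with each other?** The Study Flow Chart says that monitoring thresholds trigger the treatment strategy, so pathology determines therapy. In section 3, step 3 follows failure to improve brain oxygen. Step 4 follows failure to correct LPR and also requires low brain glucose. Step 5 follows failure of everything before it. Later therapies therefore go to patients selected for non-response. Section 8.1 further makes every aspect subject to the treating clinician's agreement in each patient.

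**3. Can a before-after fall in LPR be read as an effect?** Patients enter or trigger above 25, and success is below 25. Section 1 says that damage evolves over hours and days. The following assumes an inert treatment, and all inputs are assumptions.

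*Two readings, checkable by hand.* Take log LPR as normal, with correlation ρ between an entry reading and a later one. If the median is 25, then P(later < 25 | entry > 25) = 1/2 − arcsin(ρ)/π.

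- ρ = 0.5: 0.5 − 0.167 = 0.333
- ρ = 0.7: 0.5 − 0.247 = 0.253
- ρ = 0.9: 0.5 − 0.356 = 0.144

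Simulation with medians of 22 to 32 and an SD of log LPR of 0.3 gave 6% (median 32, ρ = 0.9) to 45% (median 22, ρ = 0.5).

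*Half-hourly series.* First-order autoregressive log LPR was simulated in 12 scenarios: median 25, 30 or 35; within-patient SD 0.1 or 0.2; autocorrelation 0.8 or 0.95; between-patient SD 0.25 throughout. Entry was either a first reading above 25 (presenting) or the first crossing within 240 readings (5 days). The next 48 readings (24 hours) were averaged. The trend was a log change of ±0.1 over 24 hours, which is exp(0.1) − 1 = +10.5% or exp(−0.1) − 1 = −9.5%.

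| Untreated trend | 24-h mean < 25, presenting | 24-h mean < 25, first crossing | Change from entry, presenting | Change from entry, first crossing |
|---|---|---|---|---|
| None | 2–19% | 7–45% | −0.3 to −7% | −0.5 to −11% |
| Upward | 1–13% | 4–36% | −2 to +5% | −7 to +5% |
| Downward | 5–27% | 11–52% | −12 to −5% | −15 to −5% |

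The last two columns use no cut-off for success. Sharing 25 as trigger and target therefore adds to the problem but does not cause it.

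**4. Who is in the cohort?** The Study Flow Chart includes a patient on LPR above 25. Section 3 aims to include all monitored patients and uses the same value as a trigger. Section 7.1.1 lists no LPR criterion. Under the assumptions above, the share not above 25 at presentation is Φ[(ln 25 − ln median)/√(0.25² + within SD²)]. For a median of 25 this is Φ(0) = 50%. For a median of 35 and within SD 0.1 it is Φ(−0.336/0.269) = Φ(−1.25) ≈ 11%. Between 0% and 20% never exceed 25 in 5 days. The two readings can therefore give quite different sets of 100 patients.

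**The case against.** The strongest reply is that the Protocol does contain comparisons. One is between pathology groups. The other is implicit: section 7.2 gives half-hourly microdialysis readings, so each patient could be compared before and after each step, and a SAP not shown here could require several readings before a step or a sustained threshold. The pathology comparison is real and should stay, but all its patients are treated and therapy follows from pathology, so it says nothing about the algorithm or the therapies. Repeated readings before a step would reduce regression to the mean. They would not supply an untreated reference for the time course.

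Other points stand in part:

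- Every input to the illustration is assumed. The 24-hour mean and the 5-day window are not in the Protocol, and at the low end the artefact is small. The conclusion does not rest on these figures.
- Objective 3 can be described by pathology; only the word implying alteration is causal.
- The bias claim in section 3 is defensible as a statement about consistent treatment.
- The entry conflict would exist with or without a control.
- The sponsor may have had a comparator in mind, in which case defining it is a legitimate alternative to relabelling. A SAP could specify a historical one, but the design label and aims here would still have to name it, and it would not remove the confounding between therapies.

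**Conclusion.** The concern holds, and the text must be corrected. The label claims a property that the described design lacks, and this follows from the Protocol's own text without any assumption. The design can establish a clinical protocol and can describe LPR, inflammation and functional outcome by pathology; objectives 2 and 4 can stand. It cannot show that the algorithm improves LPR or alters markers, nor which strategy is optimal or superior. The size of the resulting bias is not determinable from the Protocol. The simulated ranges show only that a non-trivial share of patients could reach LPR below 25 on an inert treatment, and that this share moves widely with assumptions that the study has no means of checking.

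**What to change.** 1. **Study Summary:** replace the design label with a single-arm prospective study, in line with section 6.
2. **Study Summary and sections 4, 4.1 and 4.2:** keep the aim of establishing a clinical protocol. Replace validation and improvement with a description of LPR, including whether it is below 25, after protocol steps. Reword the aim on optimal strategies, objectives 1 and 3 and the outcome as descriptive or hypothesis-generating, with no claim that the protocol caused a change or that one therapy is superior.
3. **Sections 5 and 7.2.1:** keep the comparison between pathological targets and state that it compares pathologies, not therapies.
4. **Section 3:** delete the claim about selection and researcher bias, or limit it to consistency of treatment.
5. **Study Flow Chart, section 3 and section 7.1.1:** reconcile whether LPR above 25 is an entry criterion or only a trigger, and say which patients count towards the 100.

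These changes need no extra patients or procedures. Their cost is a weaker stated claim.

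If an effect claim is wanted, name a comparator. Earlier recordings under usual management could serve as a historical one, with the same definition of an LPR above 25 episode, the same follow-up window, and an acknowledgement of drift in care. Section 7.2 calls microdialysis routine and monitored data automatically stored, which makes this plausible but does not establish that usable earlier LPR records exist. It would need data extraction and permission, because the consent section covers enrolled patients only.

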8. ETHICAL AND REGULATORY COMPLIANCE	
9. DISSEMINATION POLICY	
10. REFERENCES	
11. APPENDICES	

Directed management in brain injury.

STUDY FLOW CHART

If a patient presents with a L/P ratio >25 we will include the patient in the study. As the different monitoring thresholds are reached, it will trigger different treatment strategies in order to treat a specific pathological substrate.

Excess serum, CSF and microdialysis samples will be stored for analyses of inflammatory markers and tissue damage markers.

Follow-up at 6 months following trauma will be done through outpatient clinic.

Directed management in brain injury.

STUDY PROTOCOL

Multimodality Monitoring Directed Management of Patients Suffering from Traumatic Brain Injury

1 BACKGROUND

Traumatic brain injury (TBI) is a major cause of morbidity and mortality worldwide especially in population under 40 years of age and has a significant socioeconomic impact. TBI results from the head impacting with an object or from acceleration/deceleration forces that produce vigorous movement of the brain within the skull, with the resultant mechanical forces potentially damaging glia, neurones, axons and blood vessels. The nature of the initiating force, as well as its site, direction and magnitude, determine the type and the severity of the injury¹. Contact trauma usually results in focal injuries such as skull fractures, extradural or subdural haemorrhages and contusions. Unrestrained head movement which generates acceleration/deceleration forces usually results in diffuse axonal injury^{1,2}.

The major determinant of outcome from TBI is the severity of the primary injury, which is irreversible. However, all neurological damage does not occur at the moment of initial injury, but evolves over the ensuing hours and days. Primary injury invariably leads to the activation of cellular and molecular responses which mediate secondary injury. These include an increase in extracellular levels of glutamate leading to excitotoxicity, the onset of oxidative stress, inflammation, disruption to the blood-brain barrier (BBB) and cerebral oedema formation, all of which exacerbate injury and tissue damage³⁻¹¹. Ultimately, all this leads to brain swelling within the confines of a fixed intracranial compartment, leading to increased intracranial pressure (ICP) and compromising cerebral perfusion pressure (CPP). Current ICU protocols for the treatment of TBI focus on the treatment of secondary injury and ensuring optimal cerebral perfusion¹²⁻¹⁸.

Most specialized neurocritical care units now use multimodality monitoring which involves placing intraparenchymal probes/catheters to measure the ICP (thus enabling the calculation of cerebral perfusion pressure), brain tissue oxygen tension (PbO₂) and microdialysis, in order to minimize secondary injury. However, all current clinical protocols are ICP based, i.e. a certain ICP threshold triggers a step wise treatment approach. At present, although there is evidence base to suggest their usefulness and potential for early detection of secondary, information that microdialysis or PbO₂ monitors provide has not been implemented in clinical protocols yet.

Microdialysis is invasive monitoring which uses a semi-permeable membrane inserted into brain parenchyma to monitor the biochemistry and metabolic status of the surrounding brain tissue²⁰. The use of this technique increased our understanding of the pathophysiology of several neurological conditions. Microdialysis provides information about the energy and metabolic status of the focal area examined measuring lactate, pyruvate (and the lactate/pyruvate ratio LPR), glucose, glycerol and glutamate. After traumatic brain injury, due to ischemic/hypoxic conditions, energy production will decrease while lactate levels, and the LPR, will increase as a sign of tissue ischemia³⁸. In contrast, if pyruvate levels remain normal and lactate levels increase, ongoing mitochondrial dysfunction has been suggested³⁹. A growing body of evidence shows that microdialysis parameters (principally the lactate/pyruvate ratio) correlate with outcomes after TBI^{24,25,26}, and can be used for: early detection of secondary insults^{30,31}, monitoring and treatment of low cerebral glucose guiding systemic glucose and insulin management^{32,33,34}, monitoring during CPP augmentation/reduction and derivation of optimal CPP (CPP opt)^{35,36,37}, evaluating the effect on body temperature on cerebral chemistry²⁴. The recent International Consensus Statement from the 2014 International Microdialysis Forum²³ summarises

Directed management in brain injury.

data on the utility and prognostic power of microdialysis derived parameters and strongly supports its use in TBI treatment, but no microdialysis parameter guided clinical protocols exist to date.

2 RATIONALE

Microdialysis parameters are recognized to correlate with outcome in population studies, however they have not yet been rationalised into treatment strategies for individual patients. Further research is needed to determine which interventions may be used to modify or improve microdialysis parameters towards a goal directed target.

Given the failure to demonstrate the benefits of ICP monitoring in a large randomised trial (Chestnut *et al*, 2012) and given the number of possible neuromonitoring technique, how can an evidence base be developed for second line monitoring techniques for early detection and minimization of secondary brain injury.

3 THEORETICAL FRAMEWORK

We aim to include all traumatic brain injured patients admitted to the neuro-critical care unit that are being monitored and have multi-modality monitoring already in place. As all patients will follow the same protocol, we will minimize the risk of selection and researcher bias. As the patient will be unconscious during this process, next of kin will be asked for consent. As mentioned, this is a structured form of the standard treatments already provided in intensive care.

We will specifically identify patients in whom the microdialysis lactate:pyruvate ratio (LPR) increase above 25. This threshold has been proven to relate to a worse outcome after head injury. This will trigger our protocol which will consist of the following steps:

1. If ICP >20 mmHg, we will aim to escalate intracranial pressure decreasing measures by administering hypertonic saline (5%) 100 ml and if necessary continue on with further ICP decreasing measures.
2. If the brain oxygen pressure falls <15 mmHg, and the pressure reactivity index is >0.3 (an indication that the normal auto-regulation of the brain blood flow is not functioning properly), will increase the cerebral perfusion pressure by 10-20 mmHg.
3. If this still does not improve the brain oxygen pressure, we will increase the flow of inspired oxygen up to a maximum of 60-80%.
4. These steps do not adjust the LPR and if there is a decrease in glucose in the affected brain tissue (<1 mmol/l), we will increase the plasma glucose levels to a maximum 10 mmol/l in order to ensure that the correct amount of nutrients is being delivered, using 50% dextrose (sugar) solution.
5. If all the above steps fail to improve the LPR, it could be due to mitochondrial failure, the powerhouse of the cell. There are currently no approved therapies for this condition. However, at the treating physicians discretion, energy supplementation (e.g. succinate) or neuro-protective drugs (e.g. cyclosporine A) could be provided.

Directed management in brain injury.

Following a 6 month period, we will see the patients in our outpatient clinic to assess functional outcome. This is part of the patient's standard clinical care as all our patients are offered clinical follow up in this way.

We will collect any biological samples that are available as part of the standard clinical care of the patient and will not subject the patients to any additional procedures. This would consist of:

- left over microdialysate samples that are not used for the standard clinical care of the patient
- blood samples if the patient has an arterial line
- cerebrospinal fluid samples if the patient has an external ventricular drain inserted into the ventricles.

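### If position on the treatment ladder serves as the group label, comparing response of the lactate/pyruvate ratio between pathological states is circular, because the mitochondrial state is presumed only after that ratio has failed to respond

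*Protocol*

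**What the plan says.** Protocol section 3 starts a five-step ladder when LPR rises above 25. Steps 1 and 2 have monitored triggers that do not refer to LPR response: "If ICP >20 mmHg, we will aim to escalate intracranial pressure decreasing measures" and "If the brain oxygen pressure falls <15 mmHg, and the pressure reactivity index is >0.3". Step 3 follows if brain oxygen stays low. Step 4, the glucose step, opens differently: "These steps do not adjust the LPR and if there is a decrease in glucose in the affected brain tissue (<1 mmol/l". It combines a measured threshold with non-response to the earlier steps. Step 5 has no threshold of its own: "If all the above steps fail to improve the LPR, it could be due to mitochondrial failure".

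Section 4.2 lists one outcome: "Improvement of lactate/pyruvate ratio <25 (by different treatment strategies". Section 5 states the analysis as "comparative statistics between patients with different pathological targets", and section 7.2.1 aims the sample size at a statistical difference between those same groups. Objective 1 in section 4.1 asks which therapy best improves brain metabolism. Objectives 3 and 4 look at markers and functional outcome by pathological state. The secondary aim in section 4 calls the conditions defined, but the protocol does not list their definitions.

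Section 1 mentions a chemical pattern that does not depend on treatment: "if pyruvate levels remain normal and lactate levels increase, ongoing mitochondrial dysfunction has been suggested". Neither the ladder nor the analysis paragraph uses it.

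**The concern.** A grouping variable should be fixed before the outcome on which the groups are compared. Here the only route that the protocol gives into the mitochondrial state is failure on that outcome. If analysts label patients by the step they reached, a low LPR response in the mitochondrial group says nothing about mitochondria. It restates the entry rule. The glucose group has a milder form of the same problem, since its members have already failed to respond to the steps before it.

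This affects the one analysis that the protocol describes and the stated target of its sample size. The study could report the statistical difference it seeks between states, and a ranking of therapies under objective 1, when both come from how the groups were formed.

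**Working it through.** **The plan's own figure.** The planned size is 100. It cannot be reproduced, because section 7.2.1 gives no significance level, power, effect size, response rates or group split. The check is therefore of the logic of the label.

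**Label and outcome side by side**

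| State | How the ladder reaches it | Depends on LPR response? |
|---|---|---|
| ICP | ICP >20 mmHg | No |
| Oxygen/PRx | Brain oxygen <15 mmHg and PRx >0.3 | No |
| Glucose | Earlier steps have not adjusted LPR, and brain glucose <1 mmol/l | Partly |
| Mitochondrial | All earlier steps have failed to improve LPR | Entirely |
| Outcome (4.2) | LPR improved to <25 | It is the response |

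Under a ladder label, response to steps 1-4 in the mitochondrial group is 0 of m, whatever the biology.

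**How little it takes.** In the limiting case, all m labelled patients are non-responders and the other 100 - m all responded. Fisher's exact p is then 1/C(100, m):
- m = 1: 1/100 = 0.01
- m = 2: 1/4950 = 0.0002
- m = 10: 5.8 × 10⁻¹⁴

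**Simulation with no true mitochondrial effect.** All of the following are assumptions, since the protocol gives no rates:
- 100 patients, 1,500 runs per scenario, Fisher's exact test at two-sided 0.05.
- 30% truly mitochondrial, with no effect on LPR response or functional outcome.
- LPR response to steps 1-4 in 40%, 60% or 80% of patients.
- Favourable functional outcome in 40% of non-responders (odds 0.4/0.6 = 0.67). The odds for responders are multiplied by 1, 2 or 3, giving 40%, 57% (1.33/2.33) or 67% (2/3).
- Ladder label: every non-responder. Comparison label: true status, which is independent of response.

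Percentage of runs with p < 0.05:

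| LPR response | Odds ratio | Ladder label, LPR | Ladder label, functional | Independent label, LPR | Independent label, functional |
|---|---|---|---|---|---|
| 40% | 1 | 100 | 2.6 | 4.5 | 3.2 |
| 40% | 2 | 100 | 34.3 | 3.7 | 3.9 |
| 40% | 3 | 100 | 72.2 | 3.8 | 3.7 |
| 60% | 1 | 100 | 4.1 | 3.7 | 3.0 |
| 60% | 2 | 100 | 35.7 | 3.8 | 3.7 |
| 60% | 3 | 100 | 72.6 | 3.6 | 3.7 |
| 80% | 1 | 100 | 3.3 | 2.9 | 4.2 |
| 80% | 2 | 100 | 22.5 | 4.0 | 3.2 |
| 80% | 3 | 100 | 52.7 | 2.9 | 4.6 |

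The 100% column is a tautology and is shown for that reason. The functional column behaves differently. It keeps its nominal error when LPR response is unrelated to outcome, and rises only when the two are related. Section 1 says that LPR correlates with outcome, so some rise is plausible. Its size depends on the assumed odds ratio. The excess is a real difference between responders and non-responders, and is false only if read as an effect of mitochondrial pathology.

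**A gap in coverage.** A patient with LPR >25 who meets no threshold in steps 1-4 has had no step that could fail. Step 5 does not clearly describe this patient, although the chemical pattern in section 1 might fit.

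**The case against.** The best defence is that the allocation rule is inferred. Step 5 says only that non-response could have a mitochondrial cause, which is a bedside presumption. No sentence says that step-5 patients form an analysis group, and the study flow chart ties each pathological substrate to monitoring thresholds. Nor does the protocol say that a patient with raised ICP stops counting as an ICP patient on moving down the ladder. A statistical analysis plan may define the groups. The chemical pattern in section 1 is itself a background remark without cut-offs.

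Much of this stands, and it is why the point is conditional on ladder position being used as the label. It does not remove the point. The protocol promises defined conditions and plans to compare them, and failure to respond is the only rule it gives for recognising this one. An analysis plan that took over the ladder groups would take over the circularity.

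A reader might infer that the functional-outcome comparison is circular too. The text does not support that: the extended Glasgow Outcome Score and SF-36 play no part in step 5. The weaker statement holds, that the group is selected on a post-treatment event. The same applies to the inflammatory and damage markers, for which no calculation was made. LPR change after a step-5 treatment is also not fixed by the label; only response to the earlier steps is.

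A reader might also want the size of the spurious group. If k steps apply and each independently succeeds with probability p, the share left over is (1 - p)^k. For p from 0.6 to 0.3 this is 6-34% with three steps, 16-49% with two and 40-70% with one. The protocol gives neither p nor k, so these figures are illustrative only.

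**Conclusion.** The point holds in a limited form. If ladder position is the group label, the between-state comparison of LPR response to steps 1-4 is circular, and so is any ranking of therapies under objective 1 that relies on it. This follows from the wording and needs no numerical assumption. The glucose state shares part of the problem.

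For objectives 3 and 4, a worse result in the mitochondrial group could reflect non-response rather than pathology. Under assumed odds ratios of 2 and 3 between LPR response and favourable outcome, the chance of a misleading significant functional difference was about 22-36% and 53-73%. With no such relation it was 2.6-4.1%.

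It would go too far to conclude that the whole study is compromised. The primary aim, whether the protocol brings LPR below 25 across the cohort, needs no mitochondrial label. Comparisons of ICP with oxygen/PRx states classified at onset are also unaffected.

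**What to change.** Amend sections 4.1 and 5 for analysis only, leaving the bedside steps unchanged:

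- Classify each LPR >25 episode at its onset, before any protocol step, from the recorded ICP, brain oxygen, PRx, brain glucose, lactate and pyruvate.
- For the presumed mitochondrial group, use the pattern already cited in section 1 (raised lactate, normal pyruvate) with no other threshold met. The investigators must pre-specify the lactate and pyruvate cut-offs, since section 1 gives none.
- Allow an unclassified group, and state how episodes that meet several thresholds are handled.
- Report LPR not corrected after the applicable steps as an outcome (refractory LPR), not as a pathological state.

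The cost is wording and the choice of cut-offs. No new measurement is needed: sections 5 and 7.2 already collect these values, with microdialysis every 30 minutes. The drawback is that the mitochondrial group may be smaller than the set of patients who reach step 5, and some episodes will stay unclassified. The rule should be fixed before outcome data are examined.
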